2.3.2 Demographics and other baseline characteristics

Demographic and other characteristics at Visit Day1, including age, age group (6 years and older, < 6 years), sex, weight, height, body mass index (BMI), vital signs, and age adjusted percentile for weight and height, and z-score for height will be summarized descriptively. BMI will be calculated as weight (kg) / height² (m²) using the collected height and weight at Visit Day1.

For the calculation of z-score and age adjusted percentile, the child growth database presented by World Health Organization (WHO) (WHO global database) will be used. Z-score will be calculated using the Box-Cox power, median and coefficient of variation in the database following the procedure recommended in database instructions (WHO computation instructions).

The individual z-score (z_{ind}) for a measurement at age t is defined as:

$$z_{ind} = \frac{\left[\frac{x}{M(t)}\right]^{L(t)} - 1}{S(t)L(t)}$$

where, the Box-Cox power, median and coefficient of variation corresponding to age t are denoted by L(t), M(t) and S(t), respectively.

Final z-score is calculated as:

•
$$|z_{ind}| \le 3$$
 $z\text{-score} = z_{ind}$

•
$$z_{ind} > 3$$
 $z\text{-}score = 3 + \frac{x - M(t)[1 + 3L(t)S(t)]^{\frac{1}{L(t)}}}{M(t)[1 + 3L(t)S(t)]^{\frac{1}{L(t)}} - M(t)[1 + 2L(t)S(t)]^{\frac{1}{L(t)}}}$

$$\begin{array}{ll} \bullet & z_{ind} > 3 & z\text{-}score = \ 3 + \frac{x - M(t)[1 + 3L(t)S(t)]^{\frac{1}{L(t)}}}{M(t)[1 + 3L(t)S(t)]^{\frac{1}{L(t)}} - M(t)[1 + 2L(t)S(t)]^{\frac{1}{L(t)}}} \\ \bullet & z_{ind} < -3 & z\text{-}score = \ -3 + \frac{x - M(t)[1 + (-3)L(t)S(t)]^{\frac{1}{L(t)}}}{M(t)[1 + (-2)L(t)S(t)]^{\frac{1}{L(t)}} - M(t)[1 + (-3)L(t)S(t)]^{\frac{1}{L(t)}}} \\ \end{array}$$

Age adjusted percentile will be calculated from z-score as the probability that an observation from the standard normal distribution is less than or equal to z-score.

Relevant medical histories at Visit Dayl will be summarized, by system organ class and preferred term.

The SAF will be used for the above analyses.

2.4 Treatments (study treatment, rescue medication, concomitant therapies, compliance)

2.4.1 Study treatment / compliance

The study treatment administration is recorded on the Case Report Form (CRF) page: "Dosage Administration Record" using start date, end date, dispensing name of the study treatment and the type of change. Each pair of start date and end date will be considered as a dosing interval, if type of change is recorded as 'Dose interrupted' then this dosing interval will be considered as temporary interruptions.

Duration of exposure to the study treatment will be defined as both the treatment period including temporary interruptions and the treatment period excluding temporary interruptions and summarized for continuous variable.

Dose levels will be summarized for continuous variable by visit, regardless of the pediatric or adult dose level. In addition, the number and percentage of patients for each dose level (Dose level 1 to 4, and No treatment) will be provided by visit.

The dose level for each visit is defined as the dose level of dosing interval with its start date prior to or equal to the scheduled visit date and its end date later than or equal to the scheduled visit date. For EOS visit, actual visit date is used to identify the dose level.

In addition, the following information will be listed.

- Subject ID
- Date of Visit Day1
- Start date (Study day)

Displays the start date entered on CRF or imputed and corresponding Study day (number of days from Visit Day1).

• End date (Study day)

Displays the end date entered on CRF or imputed and corresponding Study day (number of days from Visit Day1).

- Dose Form (Granule/ Liquid/ Tablet)
- Dispensing Name (Dose Level)
- Dose administered
- Unit
- Type of Change (Dose changed/ Dose interrupted/ Dose permanently discontinued)
- Reason for Change (Adverse event/ Disease improvement under study/ Dosing error/ Dispensing error/ Technical problems/ Subject decision/ Guardian decision/ Physician decision/ As per protocol)

The SAF will be used for the above analyses.

2.4.2 Prior, concomitant and post therapies

Prior medications and significant non-drug therapies are defined as any medication or significant non-drug therapy within 30 days prior to Visit Day1 with its start date prior to the date of Visit Day1. Concomitant medications and significant non-drug therapies are defined as any medication or significant non-drug therapy with its end date later than or equal to the date of the Visit Day1 and start date prior to or equal to the end date of the treatment period.

Prior and concomitant medications and significant non-drug therapies will be summarized by anatomical therapeutic classification (ATC), preferred term.

Concomitant heart failure medications (Angiotensin converting enzyme inhibitor (ACEI), Angiotensin receptor blocker (ARB), Beta-blockers, mineralcorticoid receptor antagonists (MRAs), diuretics (excluding MRAs), Cardiac glycocytes (Digoxin/digitalis glycoside), and sodium-glucose co-transporter2 inhibitors (SGLT2i)) will be summarized by medication category and preferred term.

In addition, the prior or concomitant medications and other non-drug therapies will be listed as follows:

← Medications

- Subject ID
- Date of Study Treatment start
- Start date (Treatment day)

Displays the start date entered on CRF or imputed and corresponding Treatment day (the number of days from the date of treatment start).

• End date (Treatment day)

Displays the end date entered on CRF or imputed and corresponding Treatment day (the number of days from the date of treatment start).

• On going

If the check box of 'On going' on CRF (the medication is ongoing at the end of the study), provide 'Yes'.

- Primary indication
- ATC
- Preferred term
- Reported medication name
- Dose
- Dose unit
- Frequency
- Route

≺ Non-drug therapies

- Subject ID
- Date of Study Treatment start
- Start date (Treatment day)

Displays the start date entered on CRF or imputed and corresponding Treatment day (the number of days from the date of treatment start).

• End date (Treatment day)

Displays the end date entered on CRF or imputed and corresponding Treatment day (the number of days from the date of treatment start).

• Primary Indication

• Procedure name

The SAF will be used for the above analyses.

2.5 Analysis supporting primary objective(s)

2.5.1 Primary endpoint(s)

Any adverse events (treatment emergent or not) are considered primary endpoints.

2.5.2 Statistical hypothesis, model, and method of analysis

There are no statistical hypotheses to be tested in this study and no model analyses will be performed.

Adverse events will be summarized by primary system organ class and preferred term, using numbers and percentages of patients with at least one adverse event in the corresponding class.

The SAF will be used for analyses for primary endpoints.

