- 1. Patients who permanently discontinued the study drug treatment during PANORAMA-HF OLE study cannot be enrolled in this study (Section 5.2), however, patients who temporally discontinued the study drug for any reason at the End of Study visit (Visit 599) in PANORAMA-HF OLE study may be enrolled in this study. In this case, the assessments specified for Visit Day1 should be performed at the visit when the study treatment starts. They will have to discontinue the study unless the study treatment starts within 3 months from Visit Day1, and will be considered an early study termination (Section 5.3).
- 2. End of Study (EOS) visit will be completed when marketed product of sacubitril/valsartan pediatric formulation becomes commercially available in Japan, the study treatment is permanently discontinued based on the Investigator's judgement, or participant prematurely withdraws from the study, whichever occurs first.
- 3. Signed informed consent as well as assent at an appropriate age must be obtained prior to participation in the study. Patient Assent document is captured as a source document and is not stored in the clinical database.
- 4. If the trial is extended 1 year or over, height at Visit M12 should be recorded in the electronic Case Report Form (eCRF)
- 5. The data measured at the End of Study visit (Visit 599) in PANORAMA-HF OLE study will be utilized as the data at Visit Day1 for this study.

6. Serum sodium, potassium, creatinine, and estimated Glomerular Filtration Rate (eGFR, modified Schwartz formula) will be measured locally, and recored in the eCRF. Additional laboratory evaluation including hematology and urinalysis may be performed optionally by Investigator's clinical judgement at any visits. There is no local assessment at Visit Day1, but the results of central laboratory at the End of Study visit (Visit 599) in PANORAMA-HF OLE study should be reviewed by the Investigator soon after the results are obtained.

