7.5 Early study termination by the Sponsor

The study can be terminated by Novartis at any time. This may include reasons related to the benefit/ risk assessment of participating in the study, practical reasons (including slow enrollment), or for regulatory or medical reasons.

Reasons for early termination (but not limited to)

- Unexpected, significant, or unacceptable safety risk to participants enrolled in the study
- Decision based on recommendations from applicable board(s) after review of safety and efficacy data
- Discontinuation of study treatment development in this indication

In taking the decision to terminate, Novartis will always consider participant welfare and safety. Should early termination be necessary, participants must be seen as soon as possible and treated as a participant who discontinued from study treatment. The Investigator must provide follow-up medical care for all patients who are prematurely withdrawn from study drug or refer them for appropriate ongoing care. The Investigator may be informed of additional procedures to be followed in order to ensure that adequate consideration is given to the protection of the

participant's interests. The Investigator or Novartis depending on local regulation will be responsible for informing Institutional Review Boards (IRBs) / Independent Ethics Committees (IECs) of the early termination of the trial.

8 Study Assessments and Procedures

After identifying a potential participant, an ICF and assent (if applicable) must be signed by the parent(s)/legal guardian(s) and by the participant (as applicable) before performing any study-related procedures that are not considered standard of care for pediatric HF participants at that site. Procedures that are part of a site's standard of care for a pediatric participant or that were done as part of the End of Study visit (Visit 599) of PANORAMA-HF OLE study may pre-date the signed ICF for this study. The AE and SAE reporting period will begin at the time the ICF is signed.

The Assessment Schedule (Table 1-2) lists all of the assessments when they are performed. All data obtained from these assessments must be supported in the participant's source documentation. The "X" in the table denotes the assessments to be recorded in the clinical database or received electronically from a vendor. The "S" in the table denotes the assessments that are only in the participant's source documentation and do not need to be recorded in the clinical database.

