1.2 Study objectives, endpoints and estimands

The primary objective is to collect additional safety information of sacubitril/valsartan in the eligible Japanese patients who completed CLCZ696B2319E1 study.

There are no secondary or exploratory objectives for this study.

Table 1-1 Objectives and related endpoints

Objective(s)	Endpoint(s)	
Primary Objective(s)	Endpoint(s) for primary objective(s)	
	 Adverse events (AEs) 	

Objective(s)	Endpoint(s)
 To collect additional safety information of sacubitril/valsartan in Japanese patients after long-term treatment of sacubitril/valsartan in CLCZ696B2319E1 study 	

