2.2 Analysis sets

The following analysis sets will be used for the statistical analyses:

- Enrolled set (ENR): All patients who signed the informed consent for the extension openlabel study.
- Safety Set (SAF): All ENR patients who received at least one dose of open-label study treatment during this extension open-label study.

The number of patients and percentage for all patients who enrolled in this study will be provided for each analysis set.

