End date – Start Date + 1 will be calculated. For on-going AE, leave blank.

- Reported Name of AE
- SOC
- PT

- Relationship to study treatment (Related/ Not related)
- SAEs (Yes/No)
- Severity (Mild/ Moderate/ Severe)
- Action Taken with Study Treatment (Dose increased/ Dose not changed/ Dose reduced/ Drug interrupted/ Drug withdrawn/ Not applicable/ Unknown)
- Concomitant or additional treatment (Yes/No)
- Outcome
- TEAE (Yes/No)

The SAF will be used for the above analyses.

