2.7.2 Deaths

Death during the treatment period and the primary cause of death will be summarized using frequencies and percentages.

A listing of all deaths and heart transplant will also be provided.

The SAF will be used for the above analyses.

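### The AE listing, the death and transplant listing and the discontinuation summary are restricted to dosed participants, so post-consent events in an enrolled participant who is never dosed appear in no planned output

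*SAP*

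**What the plan says.** SAP 2.5.1 defines the endpoint broadly: "Any adverse events (treatment emergent or not) are considered primary endpoints". Collection matches that breadth. The opening text of Protocol Section 8 states: "The AE and SAE reporting period will begin at the time the ICF is signed".

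The protocol plans for enrolment without dosing. Footnote 1 to Table 1-2 (Protocol 1.3) says that "patients who temporally discontinued the study drug for any reason at the End of Study visit (Visit 599") may be enrolled. Protocol 5.3 allows the same for anyone eligible who does not start on Visit Day1. In both cases drug must start within 3 months of Visit Day1. Otherwise the participant counts as an early study termination, with the reason recorded on the disposition eCRF at Visit EOS.

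The ENR is everyone who signed consent. The SAF is "All ENR patients who received at least one dose of open-label study treatment during this extension open-label study" (SAP 2.2). For the primary AE table, SAP 2.5.2 states: "The SAF will be used for analyses for primary endpoints". SAP 2.7.1, which covers the SAE and TEAE tables and the listing of every AE, closes with "The SAF will be used for the above analyses". SAP 2.7.2 says "A listing of all deaths and heart transplant will also be provided" and closes with the same restriction. SAP 2.3.1 summarises completion, discontinuation and its reasons on the SAF.

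**The concern.** A listing described as covering all AEs or all deaths is normally where a reader looks for events that fall outside the incidence tables. SAP 2.7.1 uses the AE listing that way: events after treatment discontinuation but within the study period are not TEAEs and are sent there. For a participant who consents, is eligible and never takes a dose in this extension, that route is closed.

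The stated objective is: "The primary objective is to collect additional safety information of sacubitril/valsartan in the eligible Japanese patients who completed CLCZ696B2319E1 study". Such a participant has completed the prior study and belongs to that population. A serious event or death between consent and the planned first dose may be the reason dosing never happens. With at most 8 participants, one case of this kind would be material to the clinical study report. Under the current wording it would leave only a count in the ENR.

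**Working it through.** There is no power, alpha or sample-size figure to reproduce. The study is descriptive, and 8 is a cap. The check is a trace of analysis sets, followed by a small illustration.

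**1. Are the data collected?** Yes. Table 1-2 marks AEs/SAEs for entry in the clinical database at Day1, M3, M6, unscheduled visits and EOS. A never-starter is followed to Visit EOS.

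**2. Where could this participant appear?**

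| Output | SAP section | Analysis set |
|---|---|---|
| Analysis-set counts | 2.2 | ENR |
| Screen-failure summaries | 2.3.1 | ENR |
| Completion, discontinuation, reasons | 2.3.1 | SAF |
| Medical history | 2.3.2 | SAF |
| Medication listings | 2.4.2 | SAF |
| Primary AE table | 2.5.2 | SAF |
| SAE and TEAE tables, full AE listing | 2.7.1 | SAF |
| AEs of special interest | 2.7.1.1 | SAF |
| Death summary, death and transplant listing | 2.7.2 | SAF |
| Laboratory data, vital signs, height/weight | 2.7.3, 2.7.4 | SAF |

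No AE, SAE, death or disposition-reason output uses the ENR. The death summary is also limited to the treatment period, which never begins for this participant, so the listing was the only possible place for such a death.

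**3. Where does the restriction come from?** Protocol 9.2.2 and 9.2.3 name the SAF for baseline and treatment summaries. Protocol 9.3 and 9.6 name no set for AEs. The SAP supplies it, and SAP Section 4 records no change to the protocol analyses.

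**4. Size, as illustration only.** Assume 8 enrolled, no screen failures and one never dosed, so the SAF is 7. Let x of the 7 dosed participants have a given event.

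- The never-dosed participant has the event: all enrolled minus SAF = (x+1)/8 − x/7 = (7−x)/56. At x=0 this is 1/8 (12.5%) against 0/7 (0%). At x=1 it is 25.0% against 14.3%. At x=3 it is 50.0% against 42.9%.
- The never-dosed participant does not have the event: SAF minus all enrolled = x/7 − x/8 = x/56. At x=3 the SAF gives 42.9% against 37.5%, so the SAF figure is the higher one.

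The effect on percentages can go either way, depending on the event term. The constant result is that whatever events the never-dosed participant has are shown nowhere.

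**The case against.** A reader might infer something stronger: that the SAF removes people whose tolerability problem kept them off drug, that this biases the primary AE incidence downwards, and that the primary table should move to the ENR. The documents do not support that.

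- Visit Day1 is the same day as Visit 599. Protocol 8.6.1 sends conditions already present at consent to medical history. The event behind an interruption at Visit 599 is therefore not an AE of this study, and no change of analysis set would recover it. Only new or worsened events after consent are at issue.
- One dose in this extension is enough for the SAF. A participant who is dosed, interrupted and never restarted keeps all AEs in the tables. (The protocol-deviation exclusions in SAP Table 5-1 are a separate matter.)
- The direction of any shift varies by event term, as the second case in the working shows.
- The ENR includes screen failures. Protocol 5.3 enters no AE data for them beyond SAEs, so an any-AE percentage on the ENR would have people in its denominator whose non-serious events are not entered.
- The endpoint wording is not emptied by the SAF. Pre-dose events in delayed starters and events after the last dose are non-treatment-emergent and remain in scope.

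It is also fair to say that a dosed population is a sensible basis for incidence on a drug, that nothing is tested, and that Protocol 8.6.3 sends every SAE after consent to the sponsor's safety group within 24 hours. All of this stands. It supports keeping the tables on the SAF. It does not explain why listings presented as complete should leave out enrolled participants in a situation the protocol foresees.

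**Conclusion.** The gap is real but narrow. It is a reporting omission in the listings and the disposition summary, and it does not show that the primary incidence is biased. It applies only to a participant who consents, takes no dose in this extension and has a new or worsened event after consent. For that participant the loss from planned outputs is complete and includes the reason for discontinuation. The documents do not say how many participants, if any, were never dosed. One would be 1/8 = 12.5% of maximum enrolment, and with none the outputs are unchanged. Safety oversight of SAEs is not affected. The change is worth making because it is cheap and the current rule would drop collected events.

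**What to change.** In SAP 2.7.1 and 2.7.2, produce the AE/SAE listing and the death and heart transplant listing on the ENR, with one flag for never treated in this extension and another for screen failure. In SAP 2.3.1, summarise or list the discontinuation reasons on the ENR with the same flags.

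For never-treated participants, show Study day in place of Treatment day. Also state how partial AE dates are handled for them. SAP 5.1.2.2 imputes relative to treatment start, and the missing-start-date rule in SAP 5.1.1 should not create a start date for someone who never started.

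Keep the incidence tables (primary AE, SAE, TEAE, special interest, drug related) on the SAF. Add a footnote giving the number of enrolled, eligible, never-treated participants and how many of them had AEs or SAEs. If an incidence table wider than the SAF is wanted, base it on the ENR excluding screen failures.

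The cost is SAP wording, two flags and slightly more listing work, with no new data. The downside is that the listings will include participants with no dose in this study, which the flags make visible.

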2.5.3 Handling of intercurrent events

Not applicable.

2.5.4 Handling of missing values not related to intercurrent event

The missing value for laboratory assessments, vital signs, height, weight, and other assessments will be not imputed.

The missing or partially missing start/end date for AEs, prior/concomitant therapies, and study drug will be imputed using the Novartis ADaM Governance Board (AGB) global standard approach. Details are provided in Section 5.1.

2.5.5 Sensitivity analyses

Not applicable

2.5.6 Supplementary analyses

Not applicable

2.6 Analysis supporting secondary objectives

Not applicable. There are no secondary endpoints.

2.7 Safety analyses

2.7.1 Adverse events (AEs)

All AEs will be identified using Medical Dictionary for Regulatory Activities (MedDRA). The MedDRA version used for reporting the study will be described in a footnote.

An AE with its severity increased should be considered and recorded as a new AE.

The following adverse events will be summarized by primary system organ class, and preferred term as appropriate using numbers and percentages of patients with at least one adverse event in the corresponding class. Similarly, Summarization by maximum severity will be conducted.

- Any serious adverse event (treatment emergent or not)
- Treatment emergent adverse event (TEAE)
- Treatment emergent serious adverse event

TEAEs are defined as any recorded AE with its start date (recorded or imputed) on or after Visit Day 1 (the date of first administration of study treatment if treatment did not start at Visit Day 1) and end date as the end date of the treatment period or the date of last dose taken as reported in the DAR page. Any AE happening after treatment discontinuation but still within the study period (e.g., where patient did not discontinue the study on the same date of treatment discontinuation) would not be considered as a TEAE and will be reported in the listing of AE.

All outputs will be created for AEs regardless of study-drug relationship, and for study-drug related AEs. Study drug related AEs are defined as any recorded AE with "Relationship to study treatment" answered as "Related". Serious adverse events (SAEs) are defined as any recorded AE with "Was the adverse event serious?" answered as "Yes".

The following rules are applicable to the summaries:

- If a patient reported more than one AE with the same PT, the patient will be counted only once with the greatest severity at the PT level
- If a patient reported more than one AE within the same SOC, the patient will be counted only once with the greatest severity at the SOC level, where applicable.

In addition, the following information will be listed for all AEs.

- Subject ID
- Date of Study Treatment start
- Start date (Treatment day)

Displays the start date entered on CRF or imputed and corresponding Treatment day (the number of days from the date of treatment start).

• End date (Treatment day)

Displays the end date entered on CRF or imputed and corresponding Treatment day (the number of days from the date of treatment start).

Duration

End date – Start Date + 1 will be calculated. For on-going AE, leave blank.

- Reported Name of AE
- SOC
- PT

- Relationship to study treatment (Related/ Not related)
- SAEs (Yes/No)
- Severity (Mild/ Moderate/ Severe)
- Action Taken with Study Treatment (Dose increased/ Dose not changed/ Dose reduced/ Drug interrupted/ Drug withdrawn/ Not applicable/ Unknown)
- Concomitant or additional treatment (Yes/No)
- Outcome
- TEAE (Yes/No)

The SAF will be used for the above analyses.

